4.1 General Principles

The statistical evaluation will be performed by using the software package SAS release 9.2 or higher (SAS Institute Inc., Cary, NC, USA). Descriptive statistics will summarize the number of data available and missing data, mean, standard deviation, minimum, quartiles, median, and maximum for continuous data, and frequency tables (number of data available and missing, and percent of available data) for categorical data.

4.2 Handling of Dropouts

A “dropout” is defined as a randomized subject who discontinues study participation prior to start of study treatment for any reason.

Dropouts and subjects withdrawn from study treatment will not be replaced. Refer to Section 5.2.1 in the study protocol for withdrawal of subjects from study.

4.3 Handling of Missing Data

In order to achieve the goal of a well conducted clinical trial according to ICH Good Clinical Practice (ICH-GCP), every effort should be made to collect all data. However, despite best efforts, it may be inevitable that missing or incomplete data are reported. All missing or partial data will be presented in the subject data listing, as they are recorded on the CRF. Except as noted, missing data will not be imputed or carried forward in any statistical analysis.

4.3.1 Imputation rules

Unless otherwise specified data will not be imputed, and rules for imputation are specified in the dataset specification documents.

4.4 Interim Analyses and Data Monitoring

No interim analysis for efficacy is planned.

A Joint Safety Review Committee (JSRC) will perform monitoring for safety and protocol compliance. The JSRC will meet at regular intervals as specified by the JSRC charter, approximately every 6 months, and may decide to meet more frequently. The JSRC will be supported by an independent Statistical Analysis Center (SAC) as specified in the Charter. Reports to the JSRC will be specified in a separate document.

The conduct of the JSRC is generally similar to a Data Monitoring Committee, except that membership may include sponsor, investigator, and/or independent members, and interim results of this open-label trial may be disclosed to the sponsor. Further details are described in the JSRC charter.

4.5 Data Rules

4.5.1 Determining Baseline Values

This study has two distinct baselines for efficacy analyses, the randomization baseline and the Week 24 baseline.

Randomization baseline value for efficacy parameters: is defined as the last non-missing value on or before the date of randomization.

Week 24 baseline: Unless otherwise specified, the ‘Week 24 baseline’ is defined as the date of the 6th injection. This baseline is defined only for those subjects who are eligible for Comparison 2 analyses. That is, subjects who had received at least 6 injections.

Week 24 baseline value for efficacy parameters: Unless otherwise specified, the ‘Week 24 baseline value’ is defined as the last non-missing value on or before the date of the 6th injection.

Ideally, this visit would be the date of the 7th injection for Arm C subjects and expected 7th injection date for Arm A subjects. However, the end of treatment visit (30±7 days from last dose) for Arm A subjects could be missing due to consent withdrawal or happen out of visit window. Hence, there is no comparable visit for Arm A subjects that could be used as the expected 7th injection date.

To account for this and achieve comparability between the two arms, the 6th injection date is used as the reference date for Comparison 2 subjects. It should be noted that this could lead to a somewhat dilution of the treatment effect in Arm C due to an early reference date.

Baseline value for safety parameters: is defined as the last non-missing value on or before the date of first dose.

4.5.2 Pooling cut-off date for Arm C subjects in Comparison 1

For Comparison 1, Arm C subjects are planned to be pooled with Arm A subjects. This pooling will be done such a way that only comparable data from Arm C subject pooled. The following algorithm will be used to identify the cut-off date for pooling:

Arm C: Pooling cut-off date = $7*28 + \text{randomization date}$; for subjects that were randomized but not treated,
= $(7-x)*28 + \text{last dose date}$; for $1 \leq x \leq 6$,
= 7th dose date; for $x \geq 7$,
where x be the number of injections received.

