4.7 Additional Statistical Considerations

4.7.1 Delayed Effect Efficacy Assumptions

Since the comparison between the “standard” and “extended” regimens involves identical treatment for the first 6 doses, the following assumptions were made:

- Both regimens have identical efficacy for the first 6 doses, and
- The efficacy would diverge at the time that extended-dosing subjects received their 7th dose.

This feature is consistent with a delayed effect as described in Fine (2007) [1] and Zhang and Quan (2009) [2]. To account for this delayed-effect feature, hazards were modeled using a 2-compartment approach:

- With the standard (Arm A) and high-dose (Arm B) regimens having constant hazards throughout the study, and
- The extended regimen (Arm C) initially having the same hazards as the standard regimen (Arm A) but having a fixed change point at Week 24, approximately the point at which the 7th dose would begin, with constant, reduced hazards thereafter.

A sensitivity analysis using two-compartment Cox model will be performed by taking into account of this delayed-effect feature for Comparison 2. The details are specified in Section 6.2.1.

5. Analysis Sets

- **Intent-to-treat (ITT):** All randomized subjects. The ITT population will be used in the analysis of efficacy endpoints for Comparison 1. Subjects will be included in ITT analyses according to the treatment to which they were randomized as based on IXRS. The randomization baseline will be used in the ITT analyses.
- **Week 24(W24):** All ITT subjects in Arm A (standard dose) and Arm C (extended dosing) treated with radium-223 dichloride and eligible for further treatment at W24 (i.e., 7th injection). Week 24 applies to subjects who received the 6th injection without any dose delays. As dose delays are allowed per protocol, 6th injection can occur after Week 24 for subjects who had dose delays. Hence, this population is defined based on the number of injections not based on the timing. The W24 dataset

will be used for the analysis of efficacy endpoints related to Comparison 2 and associated evaluations. Subjects will be included in W24 analyses according to the treatment to which they were randomized.

- **Safety (SAF):** All subjects who have received at least one study drug administration. This safety population will be used in the analyses of all safety endpoints. Subjects will be included in the analyses according to the treatment they received.

6. Statistical Methodology

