9.1 Censoring Rules

9.1.1 Censoring rules for Symptomatic Skeletal Event-Free Survival (SSE-FS)

Comparison 1:

- Arm C subjects who had SSE assessments or SSE event or death (in the absence of an SSE event) after ‘pooling cut-off date’ will be censored on last SSE assessment date prior to ‘pooling cut-off date’. Refer to Section 4.5 for pooling cut-off date.
- All other subjects in arms A, B and C, refer to [Table 9–1](#) for censoring rules.
- Symptomatic Skeletal Event Free Survival (SSE-FS) following randomization = End Date – Date of Randomization +1

Table 9–1 Comparison 1: Censoring for Symptomatic Skeletal Event Free Survival (SSE-FS)

Situation	End Date	Censored	Reason for Censoring
No post-randomization SSE assessment and no death	Date of Randomization	Yes	No post-baseline SSE assessments and no death
Subject had a SSE event	Date of first SSE	No*	N/A
Death without prior SSE (<13 weeks between last SSE assessment and death) #	Date of Death	No*	N/A
Death without prior SSE (≥ 13 weeks between last SSE assessment and death) #	Last SSE assessment before the missing SSE assessments#	Yes	≥ 13 weeks between last SSE assessment and death
Neither SSE nor Death by database cutoff date	Last SSE assessment prior to database cutoff	Yes	Neither SSE nor death

*The earliest end date in the table is used in calculating the SSE-FS.

#: use randomization date instead of last SSE assessment date if no post-randomization SSE assessment.

Note: symptomatic skeletal events immediately after missing SSE assessments are still counted as events in the analysis of SSE-FS.

Comparison 2:

- All subjects eligible for Comparison 2, refer to [Table 9–2](#) for censoring rules.
- Symptomatic Skeletal Event Free Survival (SSE-FS) following Week 24 baseline= End Date – Date of Week 24 baseline(the 6th dose date) +1

Table 9–2 Comparison 2: Censoring for Symptomatic Skeletal Event Free Survival (SSE-FS)

Situation	End Date	Censored	Reason for Censoring
No SSE assessment or death following Week 24 baseline	Date of Week 24 baseline	Yes	No post-Week 24 baseline SSE assessments and no

			death.
Had an SSE event between date of randomization and Week 24 baseline	Date of Week 24 baseline	Yes	First event occurred between date of randomization and Week 24 baseline
Subject had a SSE event after Week 24 baseline	Date of first SSE	No*	N/A
Death without prior SSE (<13 weeks between last SSE assessment and death) #	Date of Death	No*	N/A

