9.1.2 Censoring rules for Overall Survival (OS)

Comparison 1:

- Arm C subjects who have died or are known to be alive after ‘pooling cut-off date’ will be censored on the ‘pooling cut-off’ date. Refer to Section 4.5 for pooling cut-off date.
- All other subjects in arms A, B and C, refer to [Table 9–3](#) for censoring rules.
- Overall Survival (OS) following randomization = End Date – Date of Randomization +1

Comparison 2

- For Comparison 2 eligible subjects, refer to [Table 9-3](#) for censoring rules.
- Overall Survival (OS) following Week 24 baseline = End Date – Date of Week 24 baseline(the 6th dose date) +1

Table 9–3 Overall Survival censoring rules

Situation	End Date	Censored	Reason for Censoring
Death on or prior to database cut off date	Date of Death	No	N/A
Not known to have died as of database cut off date	Last known alive date (LKAD) on or prior to database cutoff	Yes	No Death
Lost to follow-up prior to database cutoff	Last known alive date (LKAD)	Yes	Lost to follow up

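### The Arm C pooling cut-off for Comparison 1 depends on whether dose 7 was later given, so a death while dose 7 is delayed is always censored but survivors' delay can be pooled

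*SAP*

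**What the plan says.** Section 4.5.2 pools Arm C with Arm A up to a subject-specific cut-off and gives its aim: "This pooling will be done such a way that only comparable data from Arm C subject pooled". The cut-off has three branches:

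- never treated: randomization date + 7×28 days;
- one to six injections: last dose date + (7 − x)×28 days;
- seven or more injections: the "7th dose date; for" such subjects, with no upper limit on its lateness.

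The formula ends "where x be the number of injections received", that is, the total at the end of treatment.

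Section 5 (Week 24 set) says "As dose delays are allowed per protocol, 6th injection can occur after Week 24 for subjects who had dose delays". It gives no frequency, length or limit for delays.

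Endpoints use the cut-off differently. For SSE-FS (section 9.1.1), Arm C subjects with an assessment, SSE or death after it "will be censored on last SSE assessment date prior to ‘pooling cut-off date". For OS (section 9.1.2), "Arm C subjects who have died or are known to be alive after" the cut-off are censored on the cut-off date itself. Sections 9.1.3 to 9.1.5 also use it. Section 6.2 repeats the Comparison 1 analyses for Arm A against Arm B without Arm C, as sensitivity analyses.

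**The concern.** Before dose 7, an Arm C subject is on the same regimen as an Arm A subject. Whether his time after dose 6 + 28 days may be pooled should therefore not depend on what happens in that time. Under section 4.5.2 it does, because receipt of dose 7 sets the cut-off and a subject who dies first cannot receive it. Survival through the delay becomes a condition for pooling the delay.

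This is look-ahead censoring in the control group of a co-primary comparison. It conflicts with the section's own aim of pooling only comparable data. It also departs from the planning model in section 4.7.1, whose change point is fixed at Week 24.

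**Working it through.** **1. The plan's own figure.** Inputs from section 3.4: 186.61 events, hazard ratio 0.667, one-sided 0.10, 120 high-dose against 240 pooled subjects.

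- √(186.61 × 1/3 × 2/3) = 6.44, so SE(log HR) = 1/6.44 = 0.155.
- Power = Φ(0.405 × 6.44 − 1.282) = Φ(1.33) = 90.8%, against 90.5% stated.
- Simulation of the stated design without delay gave 186.3 events and 90.4% power.
- Event or loss by Week 24 (5.52 months): 1 − exp(−(ln 2/9 − ln 0.97) × 5.52) = 44.7%, against 44.65% stated.

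**2. The rule applied to cases.** Dose 6 on day 0; dose 7 due on day 28 but put back to day 56.

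| Arm C subject | x | Cut-off | Result |
|---|---|---|---|
| Event-free, dose 7 on day 56 | ≥7 | day 56 | days 28–56 can be pooled |
| Dies on day 40 | 6 | 0 + (7 − 6)×28 = day 28 | death censored |
| SSE on day 40, no dose 7 | 6 | day 28 | SSE censored |
| SSE on day 40, dose 7 on day 56 | ≥7 | day 56 | SSE counts |

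The last row is possible under the SAP: Table 9–2 has a row for an SSE before the 6th dose in subjects who still received that dose.

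**3. Where the dependence arises.** After dose x the cut-off lies (7 − x)×28 days ahead and the next dose is due in 28 days, so the slack is (6 − x)×28 days. It is 0 days at x=6, 28 days at x=5 and 56 days at x=4. Any delay of dose 7 triggers the problem. Dose 6 must be more than 28 days late to do so, and earlier doses more than 56.

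**4. Size when event-free time is credited up to dose 7.** Share and length of delay are assumptions. About 120 × 0.5525 = 66.3 Arm C subjects remain at Week 24. If every event in the delay prevents dose 7, events cut = 66.3 × share × (0.0770/0.1075) × (1 − exp(−0.1075 d)), with d in months. For 50% delayed 4 weeks (d = 0.92): 66.3 × 0.5 × 0.717 × 0.094 = 2.2, as in the simulation.

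| Assumed delay | Events cut | True HR 1.00 becomes | Rejection under H01 (nominal 0.10) | Power, SAP rule | Power, fixed cut-off |
|---|---|---|---|---|---|
| 25%, 4 weeks | 1.1 | about 1.01 | 0.086–0.089 | not run | not run |
| 50%, 4 weeks | 2.2 | about 1.02 | 0.074–0.081 | 88.5% | 90.6% |
| 50%, 8 weeks | 4.2 | about 1.04 | 0.060–0.066 | 86.2% | 90.9% |

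A separate paired simulation used milder delays (mean dose-7 delay 3.5 to 10 days). It cut 0.15 to 1.0 Arm C events per trial and added 5 to 19 person-months of immortal time. The hazard ratio rose by 0.1% to 0.8% for SSE-FS, and by 0.3% to 0.8% for OS with an assumed 18-month median. It set no SSE assessment schedule, so it does not settle the direction for SSE-FS.

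**5. SSE-FS when assessment timing is included.** 50% delayed 4 weeks, true HR 1.00; cells show one-sided rejection (estimated HR).

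| Events in the delay that prevent dose 7 | No SSE assessment in the delay | Assessment halfway | Assessment at dose 7 |
|---|---|---|---|
| All | 0.099 (1.001) | 0.084 (1.014) | 0.074 (1.023) |
| Half | 0.118 (0.989) | 0.105 (0.999) | 0.092 (1.009) |
| None | 0.127 (0.980) | 0.111 (0.989) | 0.099 (1.000) |

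The bottom row is a limit, since a death always prevents dose 7. With dose 6 + 28 days as the cut-off for everyone reaching dose 6, rejection was 0.093 to 0.105 in the same nine settings (Monte Carlo error about 0.003).

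**The case against.** The strongest reply concerns SSE-FS. A reader might infer that any SSE in the delay is cut, and that the co-primary hazard ratio is therefore always pushed towards 1. The documents support neither. An SSE followed by dose 7 counts. Event-free time runs only to the last SSE assessment before the cut-off; with none in the delay, a survivor gains no time while an SSE followed by dose 7 still counts. The bias then runs against the standard-dose group. This stands, and the direction is secure only for OS.

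The effect is also small. A ratio of 1.008 moves 0.667 to 0.672, or ln(1.008)/0.155 = 0.05 standard errors. The larger effects need many delays of weeks, and the SAP sentence on delays concerns the 6th injection. This stands too and keeps the point minor.

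Finally, the Arm A against Arm B analysis is free of the mechanism. That is true, but it is only a sensitivity analysis and does not repair the pooled one.

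**Conclusion.** The point holds as a minor defect. Section 4.5.2 lets later receipt of dose 7 decide how much Arm C time is pooled, and nothing elsewhere in the SAP corrects this within the pooled analysis.

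- **OS:** every death in a dose-7 delay is censored and survivors' whole delay is credited. The standard-dose hazard is understated and the high-dose hazard ratio moves upward.
- **SSE-FS:** censoring is outcome-dependent, but direction and size turn on SSE assessments during the delay and on how often dosing continues after an SSE.
- **Size:** about 0.1% to 0.8% on the hazard ratio for mean delays of 3.5 to 10 days, and up to about 4% if half the subjects were delayed 8 weeks. Delay frequency, delay length and assessment timing are all assumptions.

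**What to change.** In section 4.5.2, for seven or more injections, define the cut-off as the earlier of the 7th dose date and the 6th dose date + 28 days. Apply it to every endpoint that uses the pooling cut-off (sections 9.1.1 to 9.1.5). After dose 6, whether a day is pooled then depends only on what has already happened.

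A smaller dependence remains at x=5. The cut-off is then dose 5 + 56 days, so if dose 6 is more than 28 days late, an event after day 56 is cut while a subject who later receives dose 6 is followed on. Either state this residual or set the earlier-dose cut-offs in the same way, without using later dosing.

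The cost is one line of SAP text, one derived date and a few days of Arm C follow-up. It is a change to the analysis only; no dosing rule is touched.

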4.6 Validity Review

The results of validity review meetings will be documented in the Validity Review Reports and may comprise decisions and details relevant for statistical evaluation. Any changes to the

statistical analysis prompted by the results of the validity review meeting will be documented in an amendment and, if applicable, in a supplement to this SAP.

4.6.1 Protocol Deviations

Assessment criteria, deviation definitions, are described in a separate Protocol Deviations document.

4.7 Additional Statistical Considerations

4.7.1 Delayed Effect Efficacy Assumptions

Since the comparison between the “standard” and “extended” regimens involves identical treatment for the first 6 doses, the following assumptions were made:

- Both regimens have identical efficacy for the first 6 doses, and
- The efficacy would diverge at the time that extended-dosing subjects received their 7th dose.

This feature is consistent with a delayed effect as described in Fine (2007) [1] and Zhang and Quan (2009) [2]. To account for this delayed-effect feature, hazards were modeled using a 2-compartment approach:

- With the standard (Arm A) and high-dose (Arm B) regimens having constant hazards throughout the study, and
- The extended regimen (Arm C) initially having the same hazards as the standard regimen (Arm A) but having a fixed change point at Week 24, approximately the point at which the 7th dose would begin, with constant, reduced hazards thereafter.

A sensitivity analysis using two-compartment Cox model will be performed by taking into account of this delayed-effect feature for Comparison 2. The details are specified in Section 6.2.1.

5. Analysis Sets

- **Intent-to-treat (ITT):** All randomized subjects. The ITT population will be used in the analysis of efficacy endpoints for Comparison 1. Subjects will be included in ITT analyses according to the treatment to which they were randomized as based on IXRS. The randomization baseline will be used in the ITT analyses.
- **Week 24(W24):** All ITT subjects in Arm A (standard dose) and Arm C (extended dosing) treated with radium-223 dichloride and eligible for further treatment at W24 (i.e., 7th injection). Week 24 applies to subjects who received the 6th injection without any dose delays. As dose delays are allowed per protocol, 6th injection can occur after Week 24 for subjects who had dose delays. Hence, this population is defined based on the number of injections not based on the timing. The W24 dataset

will be used for the analysis of efficacy endpoints related to Comparison 2 and associated evaluations. Subjects will be included in W24 analyses according to the treatment to which they were randomized.

- **Safety (SAF):** All subjects who have received at least one study drug administration. This safety population will be used in the analyses of all safety endpoints. Subjects will be included in the analyses according to the treatment they received.

6. Statistical Methodology

6.1 Population characteristics

6.1.1 Disposition of Subjects

The number and percentage of subjects screened, randomized, and treated will be presented by treatment group and overall. In addition, the number of subjects discontinued prior to receiving the 6th injection in Arm A and C will be tabulated. The reasons for subjects discontinuing from treatment will be summarized by treatment group. In addition, the number of subjects screened and included in each analysis population will be displayed overall and by country and investigator.

6.1.2 Demographic and Baseline Characteristics

Descriptive summaries of demographics and baseline characteristics will be presented by treatment group and overall for the ITT, Safety and W24 populations whenever applicable. Comparability of the treatment groups with respect to demographics and baseline characteristics will be assessed using descriptive summaries.

For these tables, the summaries refer to the randomization baseline by default, using the ITT or Safety population. Additional summaries for the W24 population, using week 24 baseline, are identified below as “(W24)”. ITT population tables will be reported both by treatment arm, and by pooled arms (A & C).

The following demographic data will be summarized:

- Age (years)
- Age category (< 65, 65 – 74, 75-84, ≥85 years)
- Race and ethnicity
- Height (cm)
- Weight (kg) (W24)
- Vital signs: blood pressure (mm Hg), heart rate (bpm), respiratory rate (rpm), and temperature (°C)

The following baseline characteristics will be summarized:

- Stage of prostate cancer at initial diagnosis (TNM)
- Histology Stage of prostate cancer at study entry (TNM)

- Status of primary tumor at study entry
- Gleason score at initial diagnosis of prostate cancer
- PSA and total ALP(W24)
- ECOG Performance Status (W24)
- Number of bone lesions (1-5, 6-20, >20 but not a superscan vs. superscan at baseline)
- Bone scan lesion area
- BPI-SF average WPS (W24)
- Time from initial diagnosis to randomization for prostate cancer and bone metastases (months)
- Time from first progression to randomization for prostate cancer and bone metastases (months)
- Time from most recent progression to randomization for prostate cancer and bone metastases (months)
- Time from first progression to most recent progression for prostate cancer and bone metastases (months)

Categorical summaries of each of three randomization stratification factors per IXRS:

- Use of prior chemotherapy (≤ 1 regimen versus > 1 regimen)
- Total ALP (< 220 U/L versus ≥ 220 U/L) and
- Average worst pain score (WPS) of the BPI-SF at randomization ($WPS \leq 4$ versus $WPS > 4$), will also be presented for the ITT and W24 populations.

The discordance for each stratification factor between CRF and IXRS data will be presented in a shift table.

In addition, average WPS at randomization, as used to calculate the average WPS randomization stratification factor, will be summarized.

The following body descriptors will be summarized as described in Green and Duffull (2004) [3]:

- Total body weight(TBW), defined as the weight (kg) used for calculating the first dose
- Total body weight (W24), defined as the Week 24 baseline weight (kg)
- Body Mass Index, and Body Mass Index (W24), calculated as:

$$BMI = \frac{Weight (kg)}{[Height (m)]^2}$$

- Ideal Body Weight(IBW) will be calculated as:
 $IBW = 50.0 + [0.89 \times (HT(cm)-152.4)]$ for male

Subjects will be classified by BMI as low weight ($BMI < 18.5$), normal weight ($18.5 \leq BMI < 30$), or high weight ($BMI \geq 30$) at each baseline [4]. Baseline BMI will also be categorized as low versus normal/high.

